7.5.4 Device Removal

If at the time of a scheduled dosing it is not possible to administer a full medication dosage as per the standard administration steps detailed in the device's IFU due to a device related issue, the IDDD will be declared a device malfunction. If the device malfunction is irreversible and cannot be corrected without a device surgical intervention, the IDDD will be declared a device failure, starting from the date of the initial malfunction.

The IDDD will then be surgically removed or revised and a new device and/or device components will be re-implanted at the earliest possible opportunity, preferably at the same time.

Details of the device removal will be recorded in the patient's CRF. For further details, please refer to the SOPH-A-PORT Mini S IFU.

Patients will have the IDDD removed when they discontinue from the study, unless the patient is continuing to receive treatment through another mechanism (eg, extension study, expanded access program).

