6.8.6.7 Device Performance

Device-related terminology

- Initial device implant: The first IDDD implant that a patient ever receives.
- Partial device revision: Surgical revision/replacement of one or more component(s) of the device; other component(s) of the original device remain implanted and are not affected (e.g., port revision).
- Full device revision: The device is removed (explanted) in its entirety and a completely new device is implanted, including complete device removal with immediate replacement and delayed device implant after previous removal.
- Complete device removal with immediate replacement: Immediately implant of a new device after a device had been completely removed.
- Delayed device implant after previous removal: Implant of a new device after a previous device had been completely removed without immediate replacement on a separate and earlier occasion.
- Complete device removal without replacement: All parts of the device (both port and catheter) are removed and there is no new device implant.
- Device adjustment: surgical procedure of the device that is not a port replacement or full device revision.
- Device malfunction: The device does not perform as intended, based on the description in the device's Instructions for Use, but does not require either a partial or full device revision. If at the time of a scheduled dosing it is not possible to administer a full medication dosage as per the standard administration steps detailed in the device's Instructions for Use due to a device related issue, the IDDD will be declared a device malfunction. A device malfunction could be resolved without the need for a full or partial surgical revision. Programmatically it is when the malfunction date is present and outcome of malfunction is resolved.
- Device failure: When the device irreversibly fails to perform as intended and cannot be corrected without a device surgical intervention of either a partial or full device revision or removal. The IDDD will be declared a device failure, starting from the date of the initial malfunction that persists leading to the above surgical intervention. IDDDs that are considered to be malfunctioning at the end of the study will be categorized as Failures. For programming purposes, a device failure is when the malfunction date is present and outcome of malfunction is either ongoing or device failure (Surgical Procedure). The date of the device failure is the date of the initial malfunction.

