- IDDD longevity: Total number of IDDD failures and explant divided by the total time at risk across all subjects in weeks (sum of time to IDDD failure or the last injection if not failed at the end of the data cut or explant date, from initial implantation, delayed implantation, or revision for all IDDDs).

Device Performance Analyses

SOPH-A-PORT[®] safety and performance will be summarized for IDDD-implanted patients in Safety Population. The number and proportion of patients of the following categories and the corresponding event count and event percentage will be summarized:

- Patients who had the initial implant only (i.e., no additional surgeries)
- Patients who had any post-initial implantation device surgeries
- Patients who had any type of difficulty associated with the implant procedure (e.g., difficulty accessing spinal canal, etc)

IDDD-related surgical procedure details for initial implants, complete removal with immediate replacement, and delayed implantation across all IDDD implantations for all patients will be summarized by failed or not failed IDDDs and overall, including incision region (paramedian vs. other), identification of the catheter passer used (Phoenix Neuro vs. other), number of suture wings implanted, suture wing configuration, interspace for catheter insertion into lumbar spine (L1-2, L2-3, L3-4, L4-5, L5-S1), spinal vertebral level of catheter tip (cervical, thoracic, lumbar and sacral), use of a purse string suture, use of the guidewire, orientation of the Tuohy needle and clinical site.

The number and proportion of patients who had at least one abnormal IDDD radiological assessment finding and the number of abnormal findings from the IDDD radiological assessments will be also summarized by types of the abnormality.

The number and proportion of patients and IDDDs with total malfunctions (including failure and malfunctions) as well as the corresponding event numbers will be presented. The types of IDDD malfunctions and the reasons for IDDD failures reported by the site and the Adjudication Committee will be summarized at the patient, IDDD and event level.

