The annual event rate of IDDD failures and malfunctions will be calculated for each patient and the descriptive statistics will be summarized. The overall IDDD failure rate and its 95% CI will be presented. The overall IDDD failure rate is calculated as the total number of IDDD failures for all patients divided by the total IDDD time at risk, which is defined as the total time to IDDD failure or the last injection if IDDD is not failed at the end of the study, from initial implantation, or full device revision for all IDDDs. The overall IDDD malfunction rate is defined in the same manner.

The IDDD longevity (time to failure in weeks) and time to first total malfunction, for all implanted IDDDs, will be analyzed using the KM method. A new port identifies a new IDDD, starting from the date of implantation (either an initial implantation, a partial or full revision, or a

delayed device implant after previous removal). The time to IDDD failure (weeks) or total malfunction will be obtained by subtracting the date of the IDDD kit implantation from the date of IDDD failure (i.e., the initial malfunction date that persists leading to surgical intervention) or first total malfunction plus 1, and divided by 7, one decimal will be kept. IDDDs which did not fail or malfunction will be censored at the last study drug injection date for each IDDD. The number of IDDDs at risk, the cumulative number of IDDDs failed, censored, and the cumulative probability of failure with its standard error will be summarized in a table at each event time.

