The time from initial implant surgery to first IDDD failure and the time to first malfunction will be analyzed using the Kaplan Meier (KM) method for each patient who is in the Safety Population with IDDD implanted. The time to first IDDD failure or malfunction will be obtained by subtracting the date of the first IDDD implantation for the patient from the date of first failure or malfunction plus 1, divided by 7, and one decimal will be kept. Patients without an IDDD failure or malfunction will be censored at their last study drug injection date. The 25th percentile (Q1), median and 75th percentile (Q3) of the time to first failure or malfunction distribution and the 95% confidence interval (CI) will be presented together with the KM plots. A by-patient listing of the device failure and malfunction data will be displayed.

The IDDD longevity (time to failure in weeks) and time to first total malfunction, for all implanted IDDDs, will be plotted using the KM method. The 25th percentile (Q1), median and 75th percentile (Q3) of the time to failure or total malfunction distribution and the 95% CI will also be presented together with the KM plots.

The time (weeks) from IDDD implantation to failure/continuing function will be plotted as a horizontal bar chart for each device sorted by duration of each device implantation (time from the implantation of the corresponding IDDD), longest on top.

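### The patient-level time-to-first-malfunction curve is programmed on resolved malfunctions only, so it overstates time free of any malfunction and does not match the device-level curve

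*SAP*

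**What the plan says.** All the SAP text is in section 6.8.6.7, Device Performance.

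- **Malfunction**, in the terminology list: "Programmatically it is when the malfunction date is present and outcome of malfunction is resolved".
- **Failure**, in the same list: "a device failure is when the malfunction date is present and outcome of malfunction is either ongoing or device failure" needing a surgical procedure. On timing: "The date of the device failure is the date of the initial malfunction".
- **Total malfunction**, in the analysis text, is the wider class: "total malfunctions (including failure and malfunctions").
- **Device-level curves** cover "The IDDD longevity (time to failure in weeks) and time to first total malfunction, for all implanted IDDDs".
- **Patient-level curves** are worded differently: "The time from initial implant surgery to first IDDD failure and the time to first malfunction will be analyzed using the Kaplan Meier (KM"). They cover all implanted boys in the Safety Population.
- **Patient-level censoring** is one sentence serving both curves: "Patients without an IDDD failure or malfunction will be censored at their last study drug injection date".

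Protocol 7.14.2.2 and 7.14.2.3 make the same split: a malfunction needs no revision, and a failure needs revision or removal. Protocol 7.5.4 gives the sequence. A device that cannot deliver a full scheduled dose is first declared a malfunction; if it turns out to be irreversible without surgery, "the IDDD will be declared a device failure, starting from the date of the initial malfunction".

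**The concern.** Every failure starts as a malfunction and carries a malfunction date, yet the programming rule moves it out of the malfunction class once it proves irreversible or is still ongoing. The device-level analysis deals with this by using total malfunction. The patient-level analysis keeps the narrower word.

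A reader shown a curve titled time to first malfunction, with quartiles and confidence intervals, will take its height as the share of boys still free of malfunction. As programmed, it is the share free of a malfunction that resolved without surgery. Device safety and performance is a stated objective (Protocol 2.4), and Protocol 1.3 says this port was chosen because its predecessor failed often. A malfunction curve that does not respond to failures is a poor summary for that purpose.

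**Working it through.** The plan states no figure for this analysis, so there is nothing to reproduce. The check compares the definitions and then illustrates the size.

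**Step 1: classify each type of boy under the programming rules.**

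| Boy's device history | Patient-level failure curve | Patient-level malfunction curve, as written | Total-malfunction event |
|---|---|---|---|
| Resolved malfunction only | no event | event | event |
| Failure only (surgery, or ongoing at study end) | event, at initial malfunction date | no event | event, at initial malfunction date |
| Both | event | event, dated at the resolved malfunction, which may follow the failure | event, at the earlier date |
| Neither | censored at last injection | censored at last injection | censored at last injection |

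The second row is the problem. On the malfunction curve this boy has no event. He is not without a failure or malfunction, so the censoring sentence does not apply to him either.

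**Step 2: size, under stated assumptions.** Let M be the probability of a resolved malfunction and F the probability of a failure between implant and last injection, with independent constant hazards. The documents give neither figure for this device; all values below are assumed. The window is about 46 weeks (implant at Week 2, last injection at Week 48, Protocol 8.3).

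- Curve as written, with failure-only boys kept at risk: event-free proportion = 1 − M.
- Total malfunction: event-free proportion = (1 − M)(1 − F).
- Gap = (1 − M) × F.

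With M = 15%:

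- F = 15%: any malfunction = 1 − 0.85 × 0.85 = 27.75%, against 15% as written. Gap = 0.85 × 0.15 = 12.75 points. Of the 32 treated boys planned (SAP 4.1), that is 8.9 against 4.8.
- F = 30%: any malfunction = 1 − 0.85 × 0.70 = 40.5%, against 15%. Gap = 0.85 × 0.30 = 25.5 points, or 13.0 boys against 4.8.

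Over a wider grid (M 10% to 30%, F 10% to 50%) the gap runs from 0.70 × 0.10 = 7 points to 0.90 × 0.50 = 45 points.

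**Step 3: simulation check.** Kaplan-Meier estimates were averaged over 4,000 simulated sets of 32 boys with M = 20%.

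| F | Event-free at 46 weeks, as written | Event-free, total malfunction | Boys with a failure | Of these, not events as written | Of these, still events |
|---|---|---|---|---|---|
| 10% | 0.80 | 0.72 | 3.2 | 2.5 | 0.6 |
| 30% | 0.80 | 0.56 | 9.7 | 7.7 | 2.0 |
| 50% | 0.80 | 0.40 | 16.0 | 12.8 | 3.2 |

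The curve as written stays at 0.80 whatever the failure rate. Censoring boys at failure instead of at last injection also leaves it at about 0.80. A new censoring date alone therefore does not solve the problem; the event definition has to change.

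**The case against.** **Separate curves by severity are a coherent choice.** Protocol 10.7.7.3 already plans patient-level times to first failure and to first malfunction in similar terms, and the protocol defines malfunction as not needing revision. This stands as far as it goes. But that protocol section uses the same word at patient and device level, whereas the SAP widens it to total malfunction at device level only and gives no reason.

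**Failures are not hidden.** This stands in full. A reader might infer that boys with the worst device problem go uncounted. They do not. They are events on the patient-level failure curve and are included in the number and proportion of patients with total malfunctions, the by-patient timeline and the by-patient listing. The malfunction curve is one of many patient-level device summaries. What is missing is the patient-level timing of a first malfunction of any kind.

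**Not every boy with a failure is a non-event.** This is correct: a boy who also had a resolved malfunction is still an event, though possibly dated late.

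**Failure-only boys need not drop out.** A reader might infer that they are excluded. The SAP applies the method to every implanted patient in the Safety Population, so exclusion is not supported. Keeping them at risk is not absurd, because a failed device can be replaced and the new one can malfunction. Their handling is simply unstated.

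**A second reading exists.** The terminology also declares a device that cannot give a full dose to be a malfunction, and the censoring sentence does not censor failed boys. Both would fit counting failures as events. The explicit programming rule says otherwise, and a programmer would be expected to follow it.

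**Conclusion.** The point holds on the SAP's literal programming rules. A boy whose only device events are failures is neither an event nor assigned a censoring date on the patient-level malfunction curve. That curve overstates time free of any malfunction and does not correspond to the device-level total-malfunction curve. The two failure curves are not affected by this mismatch.

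The percentages are illustrations. They rest on assumed rates, independence and constant hazards, and they ignore the shorter window of US patients whose implantation was delayed (Protocol 8.3.1). They compare two event definitions and should not be read as a measured bias in this trial. Safety analyses are descriptive with no testing (SAP 6.8), and no efficacy result depends on this curve. The correction is worth making because the rule as written produces a curve that its title misdescribes, and putting it right is cheap.

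**What to change.** In the patient-level paragraph of SAP 6.8.6.7:

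1. Define the endpoint as time from initial implant to first total malfunction, that is, malfunction or failure, dated at the initial malfunction.
2. For this curve, censor at last study drug injection only boys with neither event.
3. Keep the time-to-first-failure curve and give it its own rule: boys without a failure are censored at last study drug injection.

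If a resolved-only curve is also wanted, its title should say so and the handling of failure-only boys should be stated. Treating failure there as a competing event is doubtful, because a replaced device can malfunction later.

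The cost is one changed event flag and a short edit to the endpoint and censoring wording. No further data are needed. Wherever there are failure-only boys, the reported malfunction-free proportion will be less favourable.

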6.8.7 Concomitant Medications

Concomitant medications for control group are defined as all medications taken on or after the date of randomization and on or before the EOS visit. Concomitant medications for IT-treatment group are defined as all medications taken on or after the date of the first IDDD implant surgery or first dose (whichever is earlier) and on or before the EOS visit (+ 30 days) or 2 weeks after the removal of the last IDDD (whichever is later).

Concomitant medications will be coded using the WHO Drug Dictionary Version September 2013 or higher. Concomitant medication use will be summarized by the Therapeutic Class and Preferred Term for each treatment group for the Safety Population.

6.8.8 Concomitant Therapies

Concomitant therapies for control group are defined as all therapies taken on or after the date of randomization and on or before the EOS visit. Concomitant therapies for IT-treatment group are defined as all therapies taken on or after the date of the first IDDD implant surgery or first dose (whichever is earlier) and on or before the EOS visit (+ 30 days) or 2 weeks after the removal of the last IDDD (whichever is later).

Concomitant therapies will be coded using the MedDRA Version 16.1 or higher and summarized by the System Organ Class and Preferred Term for each treatment group for the Safety Population.

6.9 Analysis of Pharmacokinetic Data

All pharmacokinetic analyses will be performed using the PK Analysis Population. Serum and CSF concentrations as well as pharmacokinetic parameters will be listed and summarized by treatment.

6.9.1 Concentration Data

Blood samples will be collected for determination of idursulfase serum concentration-time profiles and serum pharmacokinetic parameters after IT administration. Idursulfase concentrations in serum and CSF will be determined using a validated Enzyme-Linked Immunosorbent Assay (ELISA) method which was used for the previous idursulfase IT clinical studies. The idursulfase concentrations in serum will also be determined by a validated liquid chromatography tandem mass spectrometry (LC-MS/MS) method. The LC-MS/MS method is expected to be less susceptible to interference by anti-idursulfase antibodies.

6.9.2 Handling BLQ Values

The following procedures will be used for serum concentrations below the lower limit of quantification (LLOQ) (reported as BLQ):

- Serum samples that are BLQ are reported as zero on the data listings.
- Samples that are BLQ are treated as zero in the calculation of summary statistics (e.g., mean, SD, etc.) for the serum concentrations at individual time points.
- Mean concentrations are reported as zero if all values are BLQ, and no descriptive statistics are reported. If the calculated mean (\pm SD) concentration is less than the LLOQ, the value will be reported as calculated. The mean values derived using these conventions will be used to create the mean serum concentration versus time plots.
- For calculation of area under the serum concentration curve (AUC), BLQ values are set equal to zero in the dataset loaded into WinNonlin for pharmacokinetic analysis. WinNonlin uses the zero values that occur before the first time point with a concentration greater than LLOQ, but WinNonlin excludes the zero values from AUC calculation for all later time points.

6.9.3 Pharmacokinetic Parameters

The pharmacokinetic analysis will be conducted by the pharmacokinetics CRO for Clinical Pharmacology and Pharmacokinetics Department of Shire Pharmaceuticals using Phoenix WinNonlin version 6.2 or higher (Pharsight Corporation, Mountain View, California, USA).

Pharmacokinetic parameters will be determined from serum concentration-time data using noncompartmental methods and all calculations will be based on actual sampling times. Serum concentration vs. time will be plotted for each patient. Mean serum concentration vs. time curves will also be presented by dose (5 mg, 7.5 mg, and 10 mg) and visit (Week 4, Week 24, and Week 48).

The pharmacokinetic parameters to be determined will include, but not be limited to, the following:

C_{\max}	Maximum concentration occurring at t_{\max}
t_{\max}	Time of maximum observed concentration sampled during a dosing interval
$t_{1/2}$	Terminal half-life
$AUC_{0-\infty}$	Area under the curve extrapolated to infinity, calculated using the observed value of the last non-zero concentration
AUC_{0-t}	Area under the curve from the time of dosing to the last measurable concentration
CL/F	Total body clearance for extravascular administration divided by the fraction of dose absorbed
V_z/F	Volume of distribution associated with the terminal slope following

λ_z extravascular administration divided by the fraction of dose absorbed
First order rate constant associated with the terminal (log-linear) portion of the curve

CL/F and Vz/F will also be corrected for body weight.

Summary statistics (number of observations, mean, standard deviation, coefficient of variation, median, maximum, minimum, and geometric mean) will be determined for all pharmacokinetic parameters and presented by bioanalytical method (ELISA, LC-MS/MS), dose and visit. Serum and CSF concentrations of idursulfase at each nominal sampling time will also be summarized by bioanalytical method, dose and visit using descriptive statistics.

The association of the presence of anti-idursulfase antibodies and idursulfase concentration-time profiles and pharmacokinetic parameters will be evaluated, if applicable.

6.10 Drug-Drug and Drug-Disease Interactions

The study is not designed to evaluate drug-drug or drug-disease interactions and therefore the interactions will not be assessed in this study.

7. CHANGES IN THE CONDUCT OF THE STUDY OR PLANNED ANALYSES

7.1 Changes in the Conduct of the Study

Please see the amendment summaries for the HGT-HIT-094 Protocol.

7.2 Changes from the Analyses Planned in the Protocol

The changes from the analyses planned in the protocol included

- Changing in subgroup age cut off from <7 to <6
- Adding interaction terms in the MMRM modelling
- Adding a sensitivity analysis for the primary analysis using ITT population excluding subjects enrolled from the observational study HGT-HIT-090 who experienced a decrease in GCA score of ≥ 10 points over 12 months in study HGT-HIT-090 prior to being enrolled in study HGT-HIT-094 and a GCA score at HGT-HIT-094 Screening >85
- Adding MMRM modeling for T scores of six core subtests from DASII EY
- Adding subgroup analysis for the subgroup with baseline age < 6 years
- Adding subgroup analysis for the subgroup with baseline GCA ≤ 70 and baseline GCA > 70
- Adding subgroup analysis for the subgroup with baseline age < 55 months and baseline age ≥ 55
- Adding rate of change in GCA score analysis
- Changing non-parametric Wilcoxon Rank Sum test to van Elteren (vE) test

